Appendix C - Laboratory Values

Table C1 Abnormal Laboratory Values Rating: Serum Chemistry Parameters

Serum Chemistry	Mild (Grade 1)	Moderate (Grade 2)	Severe (Grade 3)	Life-Threatening (Grade 4)
Sodium – Hyponatremia (mmol/L) ^a	<LLN - 130	-	<130 - 120	<120
Sodium – Hypernatremia (mmol/L) ^a	>ULN - 150	>150 - 155	>155 - 160; hospitalization indicated	>160
Potassium – Hyperkalemia (mmol/L) ^a	>ULN - 5.5	>5.5 - 6.0	>6.0 - 7.0; hospitalization indicated	>7.0
Potassium – Hypokalemia (mmol/L) ^a	<LLN - 3.0	<LLN - 3.0; symptomatic; intervention indicated	<3.0 - 2.5; hospitalization indicated	<2.5
Glucose – Hypoglycemia ^a (mg/dL) (mmol/L)	<LLN – 55; <LLN – 3.0	<55 – 40; <3.0 – 2.2	<40 – 30; <2.2 – 1.7	<30; <1.7
Glucose – Hyperglycemia: ^a Fasting (mg/dL) (mmol/L)	>ULN-160; >ULN-8.9	>160-250; >8.9-13.9	>250-500; >13.9-27.8; hospitalization indicated	>500; >27.8
Creatinine increased ^a	>1 – 1.5 x Baseline; >ULN – 1.5 x ULN	>1.5 – 3.0 x Baseline; >1.5 – 3.0 x ULN	>3.0 x Baseline; >3.0 – 6.0 x ULN	>6.0 x ULN
Albumin - Hypoalbuminemia ^a (g/dL) (g/L)	<LLN – 3; <LLN – 30	<3 – 2; <30 – 20	<2; <20	- -
Alkaline phosphatase increased ^a	>ULN – 2.5 x ULN	>2.5 – 5.0 x ULN	>5.0 – 20.0 x ULN	>20.0 x ULN
ALT / AST increased ^a	>ULN – 3.0 x ULN	>3.0 – 5.0 x ULN	>5.0 – 20.0 x ULN	>20.0 x ULN
Gamma-glutamyl transferase (GGT) increased ^a	>ULN – 2.5 x ULN	>2.5 – 5.0 x ULN	>5.0 – 20.0 x ULN	>20.0 x ULN
Blood bilirubin increased (total and direct) ^a	>ULN – 1.5 x ULN	>1.5 – 3.0 x ULN	>3.0 – 10.0 x ULN	>10.0 x ULN
Cholesterol high ^a				

Confidentiality Statement

Data and information contained in this document are considered to constitute trade secrets and confidential commercial information, and the legal protections provided to such trade secrets and confidential information are hereby claimed under the provisions of applicable law. No part of this document may be publicly disclosed without the written consent of Philip Morris Products S.A.

Serum Chemistry	Mild (Grade 1)	Moderate (Grade 2)	Severe (Grade 3)	Life-Threatening (Grade 4)
(mg/dL) (mmol/L)	>ULN - 300; >ULN - 7.75	>300-400; >7.75-10.34	>400-500; >10.34-12.92	>500; >12.92
Triglycerides - Hypertriglyceridemia ^a				
(mg/dL) (mmol/L)	150 – 300; 1.71 – 3.42	>300 – 500; >3.42 – 5.70	>500 – 1000; >5.70 – 11.40	>1000; >11.4

Abbreviations: ALT = Alanine aminotransferase; AST = Aspartate aminotransferase; BUN = Blood urea nitrogen; GGT = Gamma-glutamyl transferase; LLN = Lower limit of the normal range; ULN = Upper limit of the normal range.

Data Sources:

^a Common Terminology Criteria for Adverse Events (CTCAE) version 4.03. Toxicity Grading Scale for Healthy Adult and Adolescent Volunteers Enrolled in Preventive Vaccine Clinical Trials, U.S. Department of Health and Human Services, FDA, Center for Biologics Evaluation and Research - Guidance for Industry.

Table C2 Abnormal Laboratory Values Rating: Hematology Parameters

Hematology	Mild (Grade 1)	Moderate (Grade 2)	Severe (Grade 3)	Life-Threatening (Grade 4)
Anemia (Hemoglobin) ^a (g/dL) (mmol) (g/L)	<LLN-10.0 <LLN-6.2 < LLN-100	<10-8.0 <6.2-4.9 < 100-80	<8.0 <4.9 <80 Transfusion indicated	Life threatening consequences; urgent intervention indicated
Hemoglobin increase ^a – (g/dL)	Increase in >0 – 2 above ULN or above Baseline if Baseline is above ULN	Increase in >2 – 4 above ULN or above Baseline if Baseline is above ULN	Increase in >4 above ULN or above Baseline if Baseline is above ULN	-
WBC Decrease ^a – (cell/mm ³) (10 ⁹ /L)	<LLN – 3000; <LLN – 3.0	<3000 - 2000; <3.0 – 2.0	<2000 - 1000; <2.0 – 1.0	<1000; <1.0
Lymphocytes increase ^a (cell/mm ³)	-	>4,000 – 20,000	>20,000	-
Lymphocytes decrease ^a (cell/mm ³) (10 ⁹ /L)	<LLN – 800; <LLN – 0.8	<800 - 500; <0.8 – 0.5	<500 - 200; <0.5 – 0.2	<200; <0.2

Confidentiality Statement

Data and information contained in this document are considered to constitute trade secrets and confidential commercial information, and the legal protections provided to such trade secrets and confidential information are hereby claimed under the provisions of applicable law. No part of this document may be publicly disclosed without the written consent of Philip Morris Products S.A.

Hematology	Mild (Grade 1)	Moderate (Grade 2)	Severe (Grade 3)	Life-Threatening (Grade 4)
Neutrophils Decrease ^a (cell/mm ³) (10 ⁻⁹ /L)	<LLN – 1500; <LLN – 1.5	<1500 - 1000; <1.5 – 1.0	<1000 - 500; <1.0 – 0.5	<500; <0.5
Platelets decrease ^a (cell/mm ³) (10 ⁻⁹ /L)	<LLN – 75,000; <LLN – 75.0	<75,000 – 50,000; <75.0 – 50.0	<50,000 – 25,000; <50.0 – 25.0	<25,000; <25.0

Abbreviations: LLN = Lower limit of the normal range; ULN = Upper limit of the normal range; WBC = White blood cell.

Data Source:

^a Common Terminology Criteria for Adverse Events (CTCAE) version 4.03. Toxicity Grading Scale for Healthy Adult and Adolescent Volunteers Enrolled in Preventive Vaccine Clinical Trials, U.S. Department of Health and Human Services, FDA, Center for Biologics Evaluation and Research - Guidance for Industry.

Table C3 Abnormal Laboratory Values Rating: Urine analysis Parameters

Urine	Mild (Grade 1)	Moderate (Grade 2)	Severe (Grade 3)	Life-Threatening (Grade 4)
Protein ^a	1+ proteinuria; urinary protein <1.0 g/24 hours	2+ proteinuria; urinary protein 1.0- 3.4 g/24 hours	Urinary protein ≥3.5 g/24 hours	-

Data Source:

^a Common Terminology Criteria for Adverse Events (CTCAE) version 4.03. Toxicity Grading Scale for Healthy Adult and Adolescent Volunteers Enrolled in Preventive Vaccine Clinical Trials, U.S. Department of Health and Human Services, FDA, Center for Biologics Evaluation and Research - Guidance for Industry.

Confidentiality Statement

Data and information contained in this document are considered to constitute trade secrets and confidential commercial information, and the legal protections provided to such trade secrets and confidential information are hereby claimed under the provisions of applicable law. No part of this document may be publicly disclosed without the written consent of Philip Morris Products S.A.

Appendix D – Human Puffing Topography Parameters

Table D1 Per-puff parameters

Description	Variable	Unit
Puff number	Ni	
Puff volume	Vi	mL
Puff duration	Di	s
Average flow [Vi/Di]	Qmi	mL/s
Peak flow	Qci	mL/s
Inter puff interval	li	s
Sum of li and Di	DFi	s
Peak flow position	PosQci	%
Number of peaks	Pn	

Table D2 Per-product use experience parameters

Description	Variable	Formula	Unit
Total number of puffs	NPC	Σ Ni	
Total puff volume	TVOL	Σ Vi	mL
Average puff volume	AvgVi	Σ Vi / NPC, i=1 ... NPC	mL
Average puff duration	AvgDi	Σ Di / NPC, i=1 ... NPC	s
Total puff duration	TDi	Σ Di	s
Average flow	AvgQmi	Σ Qmi / NPC, i=1 ... NPC	mL/s
Peak flow	AvgQci	Σ Qci / NPC, i=1 ... NPC	mL/s
Total inter puff interval	Tli	Σ li	s
Average inter puff interval	Avgli	Σ li / NPC, i=1 ... NPC	s
Total puffing duration	TDFi	Σ DFi	s
Puffing Intensity	SMINT	TVOL/TDFi	mL/s
Puffing Time Index	PTI	(100*TDi)/TDFi	%
Puff Frequency	PFeq	NPC/(TDFi/60)	

Confidentiality Statement

Data and information contained in this document are considered to constitute trade secrets and confidential commercial information, and the legal protections provided to such trade secrets and confidential information are hereby claimed under the provisions of applicable law. No part of this document may be publicly disclosed without the written consent of Philip Morris Products S.A.

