6.2.2 Investigational Period (Day 1 to Day 5)

Each subject will use P3P 3 on Day 1. In the morning of Day 2, subjects will be randomized to one of six sequences in order to cross-over to the use of P3P 1, P3P 2 and P3P 4 on Days 2, 3 and 4 (section 6.3).

On each assessment day (Day 1 to Day 4), following at least 10 hours of abstinence from any tobacco and nicotine containing products, subjects will use the assigned product for the given visit with two product use regimen as described in Figure 2:

- using a fixed puffing regimen comprising of 12 puffs in total at a rate of one inhalation every 30 seconds (\pm 5 seconds) in the morning.
- using *ad libitum* use period for 60 minutes (\pm 5 minutes) in the afternoon.

A puffing topography device will be attached to each P3P. There will be one recording of HPT parameters per product. Each P3P product will be weighed before and after product use to estimate the amount of nicotine delivered in the aerosol. During the *ad libitum* use period, the subjects can use the product according to their puffing behavior, without restrictions in the number of puffs, interpuff interval duration or number of products used. The number of P3P products used during the *ad libitum* use period will be recorded. The start and stop time of each product used during each puffing regimen will be recorded as well as the total number of puffs taken at the fixed puffing regimen.

The start of product use for fixed puffing and for the *ad libitum* use period will be defined as T_0 fix and T_0 ad lib, respectively. There will be a washout period of 10 hours between T_0 fix and T_0 ad lib.

There will be no product use on the Discharge day (Day 5).

Except for the assigned products, subjects will not be allowed to use any nicotine-containing products through Discharge or early termination.

Subjects will be continuously supervised by the investigational site staff during P3P use.

Confidentiality Statement

Data and information contained in this document are considered to constitute trade secrets and confidential commercial information, and the legal protections provided to such trade secrets and confidential information are hereby claimed under the provisions of applicable law. No part of this document may be publicly disclosed without the written consent of Philip Morris Products S.A.

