7.9 Other Study Procedures

7.9.1 Human Puffing Topography

Human puffing topography involves the measurement of each subject's unique way of using P3P using the HPT SODIM® device. The HPT SODIM® device, model SPA/M (SODIM® Instrumentation, Fleury les Aubrais, France) is a device which is used to measure puffing topography. It consists of a special sample holder with mechanical adapter and a data logger. Both the sample holder and the mechanical adapter are associated prior the activation of the P3P, and its insertion into the mechanical adapter using a depth adjustment tool. The sample holder is connected by 2 narrow tubes to the portable data logger/recording system. Any malfunction of the HPT SODIM® portable device will be documented in the appropriate log.

The HPT SODIM® device has to be used for every P3P used for all subjects from Day 1 to Day 4, both during the fixed puffing and the *ad libitum* use period. For each subject, one HPT Device will be assigned at Day 1 which will be used by that subject for all HPT assessments. A replacement device will be provided in case of malfunction of the device assigned.

The Sponsor will provide training on the use of the HPT SODIM® device to the site collaborators which will be responsible for the HPT assessment. All HPT SODIM® devices will be returned to the Sponsor after completion of the study.

The HPT SODIM® device measures and records the flow rate and other per-puff parameters listed in Appendix D. From the per-puff parameters, per-product use experience parameters, representing average or total values per product, will be derived (Appendix D).

Prior to calculation of the per-product use experience parameters, the Sponsor's HPT group will process, validate and discard any invalid data, as per the Sponsor's SOPs. The Sponsor will provide copies of both the raw and validated HPT datasets to the Investigator. Only valid data for the per-puff and per-product use experience parameters will be part of the study database and will be analyzed.

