9.3 Investigational Period (Day 1 to Day 4)

At each assessment day subjects will use the assigned product for the given visit with two product use regimen:

- fixed puffing regimen comprising of 12 puffs in total at a rate of one inhalation every 30 seconds (\pm 5 seconds) in the morning.
- ad libitum* use period for 60 minutes (\pm 5 minutes) in the afternoon.

The study activities performed in the morning (prior to and related to fixed puffing) for Days 1, 2, 3 and 4 are listed in Table 9. The study activities performed in the afternoon (related to *ad libitum* product use and post product use activities) are listed in Table 10. The start of each product use regimen will be separated by at least 10 hours.

Table 9 Time Schedule – Fixed puffing period (Day 1, 2, 3, 4 - Morning)

Time	Blood Sample	Procedures	Additional Information
Start of Procedure			
Prior to product use	✓	Blood sampling for CYP2A6 assessment	Day 1 only
Prior to product use	✓	Clinical laboratory parameters (hematology, clinical chemistry)	After at least 6 hours of fasting. Day 2, 3 and 4
Prior to product use		Urine analysis safety panel	Day 2, 3 and 4
Prior to product use		Cough assessment	Day 2, 3 and 4. 24 ± 1 hour after T_0 fix for the product used on the previous day
Prior to product use at Day 2		Randomization	Day 2 only. Discontinuation of supernumerous subjects, if applicable, should occur prior to randomization
Prior to product use (within 2 hours)		Assembly and weighing of product	
Prior to product use (within 1 hour)		Vital signs (blood pressure, pulse rate, respiratory rate)	At least 5 min in supine position prior to measurement.
15 \pm 5 minutes prior to T_0 fix	✓	Blood sampling for baseline nicotine level for fixed puffing	

Confidentiality Statement

Data and information contained in this document are considered to constitute trade secrets and confidential commercial information, and the legal protections provided to such trade secrets and confidential information are hereby claimed under the provisions of applicable law. No part of this document may be publicly disclosed without the written consent of Philip Morris Products S.A.

Time	Blood Sample	Procedures	Additional Information
Start of Procedure			
15 ± 5 minutes prior to T_0 fix		VAS-craving: baseline for fixed puffing	
Just before product use		Piercing of P3P capsule	

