**Table 12 Human Puffing Topography Parameters Per-Product Use**

Description	Variable	Formula	Unit
Total number of puffs	NPC	$\Sigma N_i$	
Total puff volume	TVOL	$\Sigma V_i$	mL
Average puff volume	AvgVi	$\Sigma V_i / NPC, i=1 \dots NPC$	mL
Average puff duration	AvgDi	$\Sigma D_i / NPC, i=1 \dots NPC$	sec
Total puff duration	TDi	$\Sigma D_i$	sec
Average use flow	AvgQmi	$\Sigma Q_{mi} / NPC, i=1 \dots NPC$	mL/sec
Average peak flow	AvgQci	$\Sigma Q_{ci} / NPC, i=1 \dots NPC$	mL/sec
Total inter puff interval	Tli	$\Sigma I_i$	sec
Average inter puff interval	Avgli	$\Sigma Q_{ci} / NPC, i=1 \dots NPC$	sec
Total puffing duration	TDFi	$\Sigma D_{fi}$	sec
Puffing Intensity	SMINT	TVOL/TDFi	mL/sec
Puffing Time Index	PTI	$100 * TDi / TDFi$	%
Puff Frequency	PFeq	$NPC / (TDFi / 60)$	

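### The average inter-puff interval is divided by the number of puffs, although n puffs enclose only n-1 intervals and the value for the unpaired puff is undefined

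*Protocol*

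**What the plan says.** Protocol Appendix D, Table D1 lists the inter-puff interval li among the per-puff parameters, together with DFi, described as "Sum of li and Di". Table D2 then derives per-product values. The average interval is "Σ li / NPC, i=1 ... NPC", where NPC is labelled as the total number of puffs. The sum of DFi gives the total puffing duration, TDFi, which is the denominator of puffing intensity (SMINT), puffing time index (PTI) and puff frequency (PFeq).

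SAP section 7.4, Table 12 keeps the row "Total inter puff interval" and the same SMINT, PTI and PFeq formulas. For the average interval it prints the sum of Qci, the peak flow, over NPC, while labelling the result in seconds.

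The unit of recording is the product: "There will be one recording of HPT parameters per product" (Protocol 6.2.2). The fixed regimen is "12 puffs in total at a rate of one inhalation every 30 seconds"; ad libitum use is "without restrictions in the number of puffs, interpuff interval duration or number of products used". Before the per-product values are calculated, the sponsor's topography group will "process, validate and discard any invalid data, as per the Sponsor's SOPs" (Protocol 7.9.1).

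Neither document says whether li is measured before or after its puff, or what it takes for the puff at the open end of the recording.

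**The concern.** Intervals between puffs number one fewer than puffs. A formula that runs i from 1 to NPC and divides by NPC needs one more value than there are gaps. Something must fill that place, and whatever fills it goes into the average. An absent or zero value makes the average too short. Lead-in or trailing recording time makes it include time that is not between puffs.

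Topography is secondary objective 3 and is summarised by variant. A bias common to all variants would be a nuisance only. A bias that depends on the number of puffs per product could make two variants look different in ad libitum use when the puffing pace is the same. Replacing the Qci numerator in SAP Table 12 with the protocol's li would leave this problem in place.

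**Working it through.** **Inputs**

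- Puffs per product, n (= NPC, read as a count): 12 in the fixed regimen (Protocol 6.2.2 and 9.3). Unrestricted in ad libitum use; the values 5, 8, 20 and 30 below are illustrations, since the documents give no counts.
- Start-to-start cycle, C: 30 s, with a window of ±5 s (same sections).
- Puff duration, D: not given. Assumed 2 s, with 1 to 5 s as the range.
- True interval: I = C - D = 28 s.
- Coding of li for the unpaired puff: not given, so each possibility is worked through.

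The documents state no numerical value for any topography parameter. The only benchmark is the planned pace, 60/30 = 2.0 puffs/min.

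**1. Unpaired interval missing or zero.** The sum holds n-1 intervals and the divisor is n:

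Avgli = (n-1) × I / n, so Avgli / I = (n-1)/n, a shortfall of exactly 1/n.

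| n | Sum of intervals (s) | Avgli (s) | True mean (s) | Error |
|---|---|---|---|---|
| 5 | 4 × 28 = 112 | 22.4 | 28.0 | -20% |
| 8 | 7 × 28 = 196 | 24.5 | 28.0 | -12.5% |
| 12 | 11 × 28 = 308 | 25.67 | 28.0 | -8.3% |
| 20 | 19 × 28 = 532 | 26.6 | 28.0 | -5% |
| 30 | 29 × 28 = 812 | 27.07 | 28.0 | -3.3% |

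The relative error does not depend on C or D. At n=12 a 25 s cycle gives 21.08 s against 23 s, and a 35 s cycle gives 30.25 s against 33 s, both -8.3%. With C = 30 s, D = 1 s gives 26.58 s against 29 s, and D = 5 s gives 22.92 s against 25 s, again -8.3%.

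**2. Unpaired interval equals time T to the start or end of the recording.** At n=12, Avgli = (308 + T)/12. This equals 28.0 s only if T happens to be 28 s. Otherwise the average moves with when the recording was started or stopped.

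**3. Effect on comparisons between variants, in case 1.** In the fixed regimen n = 12 for every variant, so each mean carries the factor 11/12 and ratios between variants are unaffected. In ad libitum use the factor follows n. Two variants puffed at the same pace, one with 6 puffs per product and one with 12, would differ by (5/6)/(11/12) = 0.909, about 9% in Avgli from the divisor alone. With 5 against 20 puffs the ratio is 22.4/26.6 = 0.842, about 16%.

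**4. TDFi and the ratios built on it, at n=12.**

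- If the unpaired li is zero, TDFi = 308 + 12 × 2 = 332 s. The last puff starts at 11 × 30 = 330 s and ends at 332 s, so TDFi is exactly the time from the start of the first puff to the end of the last. PFeq = 12/(332/60) = 2.17 puffs/min and PTI = 24/332 = 7.23%.
- If the unpaired DFi is dropped as missing, TDFi = 11 × 30 = 330 s and PFeq = 12/(330/60) = 2.18 puffs/min. One puff is then in the numerator but its duration is not in the denominator.
- If the unpaired puff carries a further 28 s, TDFi = 12 × 30 = 360 s and PFeq = 2.00 puffs/min.

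The coding of the unpaired puff therefore decides which span TDFi covers.

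**The case against.** The strongest reply is that the table is consistent as printed: li is a per-puff parameter, it is indexed to NPC and divided by NPC. If each of the 12 puffs carried a 28 s interval, Avgli would be 336/12 = 28.0 s and PFeq 2.00 puffs/min, matching the plan. Dividing that same sum by NPC-1 would then create an error, 336/11 = 30.5 s. The sponsor's SOPs, which are not supplied, may also settle the end value.

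Part of this stands. How the device export codes the unpaired puff is not documented, so the shortfall of 1/n is conditional. But the no-error reading needs the unpaired puff to carry a full ordinary interval, and no section says so. The risk of dividing wrongly disappears if the sum as well as the divisor is restricted to the NPC-1 true gaps. The SOPs are described as covering processing, validation and discarding of invalid data; that does not replace a definition in the table.

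A reader might also infer that PFeq, SMINT and PTI are overstated, by +8.4% at n=12 on the assumptions above. The documents do not support that. With n-1 gaps and the unpaired puff's own duration kept, TDFi is elapsed time from the start of the first puff to the end of the last. Puffs, volume or puffing time over that span is a legitimate definition. It differs from a per-cycle rate without being wrong.

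Nor should the impact be read as larger than it is. Protocol 12.6.2.4 and SAP 12.6.3 plan descriptive summaries of topography, with no model or contrast between variants, and the study tests no hypothesis. The bias can differ between variants only in ad libitum use, and only if puffs per product differ.

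**Conclusion.** The concern holds for the average inter-puff interval. As written, the rule either divides n-1 gaps by n or averages in a segment that lies between no two puffs, and the documents do not say which.

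In the first case Avgli is low by exactly 1/n: -8.3% at n=12, -20% at n=5, -5% at n=20. The percentages rest only on the unpaired value being missing or zero; the figures in seconds also rest on a 30 s cycle and assumed 2 s puffs. In the second case the size cannot be stated without knowing how recordings are started and stopped. The fixed-regimen ratios between variants are unaffected in the first case; ad libitum comparisons can be affected.

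For PFeq, SMINT and PTI the gap is only that the span of TDFi is not stated. This is a definitional correction to a descriptive secondary endpoint, worth making before the per-product values are derived.

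**What to change.** In Protocol Table D2 and SAP Table 12:

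1. Define Avgli as the sum of the NPC-1 true between-puff intervals divided by NPC-1, and missing if NPC = 1. Restrict both the sum and the divisor. In SAP Table 12 this replaces the Qci numerator at the same time.
2. State whether li precedes or follows its puff, and how li and DFi are coded for the unpaired puff.
3. Keep the PFeq, SMINT and PTI formulas, and state that TDFi runs from the start of the first puff to the end of the last. Add a note that PFeq on this span exceeds the per-cycle pace: about 2.17 against 2.0 puffs/min at n=12 with a 30 s cycle and 2 s puffs.

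The cost is table wording and a small change to the derivation program; no new data are needed. The downside is that Avgli will not be directly comparable with any earlier sponsor study that divided by NPC. The value with the NPC divisor can be listed alongside.

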### 3 INTRODUCTION

This SAP has been developed to supplement the statistical analyses described in the clinical study protocol final version 1.0 dated 24 July 2017.

This SAP describes the methodology and considerations of the planned analyses and a list of all the TFLs for this study. A detailed description of the planned TFLs will be provided in a separate TFL shells document. Any changes to the TFL shells numbering or to the title of the TFLs will not require an amendment to this SAP.

This SAP and any amendments will be finalized prior to the lock of the clinical database. Any changes to the analyses described in this document or additional analyses performed to supplement the planned analyses, will be described in the clinical study report (CSR).

The preparation of this SAP is based on the following documents:

- International Conference on Harmonisation (ICH) E9 guideline entitled, "Guidance for Industry: Statistical Principles for Clinical Trials" (**ICH Guideline E9, 1998**).
- ICH E3 guideline entitled, "Guidance for Industry: Structure and Content of Clinical Study Reports" (**ICH Guideline E3, 1995**).
- Case report forms (CRF) final version 1.0 dated 25 AUG 2017.
- Randomization Plan version 2.0 dated 16 OCT 2017.

